## **1. STUDY OBJECTIVES**

### **1.1 Primary Objective**

#### **Objective 1: Enhance efficiency of recruitment, engagement, and retention across sites.**

We will successfully enroll 52 LEOs at Albuquerque, 26 at Portland, and 26 at Madison, with an *across-site average* of 20% female and 35% racial/ethnic minority participants; 85% of participants will attend  $\geq$  6 MBRT or SME sessions (i.e., treatment completer), and complete 75% of assigned homework. Based on 80% retention at *3 months* in the recent R21, enhanced retention efforts will result in  $\geq$  80% at *6 months*.

Per NCCIH SARP guidelines, we will gauge accrual and retention by accrual of  $\geq$  80% but no higher than 150% of benchmark number at a given time point, study initiation delay of  $\leq$  1 accrual reporting period ( $\sim$ 4 months), and actual loss to follow-up rate  $\leq$  20%.

**Objective 2: Ensure fidelity and equivalence of lab, assessment, and data management procedures across sites.** 100% of staff will complete trainings in research ethics, an NIH Good Lab Practice course, and all assessment and lab procedures. Throughout the study, there will be  $\leq$  5% rate data procedural errors, tracked in REDCap (same procedure used in R21 study). Based on the R21 study, we expect  $\leq$  15% missing data due to omitted or refused completion of measures from active participants. Collection of self-report measures will be acceptable to LEOs at all sites, i.e., all assessments will be completed in the allotted time, assessment burden will be acceptable, and questionnaire items will be relevant and acceptable ( $\geq$  75% of LEOs rate assessment protocol as “reasonable” or “very reasonable” in content, clarity and time burden). We will obtain departmental excessive use of force (i.e., BlueTeam or other departmental data) for 100% of participants at all sites in designated period (1 month to assemble pre-baseline, and 1 month to assemble at 12-month follow-up). Biweekly reviews will yield 100% adherence to data management protocol at both data collection sites.

**Objective 3: Optimize intervention training procedures and ensure fidelity to intervention protocols across sites.** All study MBRT and SME interventionists will complete intensive clinical trainings, demonstrate 90% fidelity on Adherence and Competence scales, and

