#### **Objective 4: Assess participant experience and optimize outcome measures across sites.**

Well-developed content themes with data saturation emerging from feedback interviews will provide information on acceptability, impact of assessments, protocol and intervention fidelity, and equivalence of these markers across sites. Benchmark sensitivity and responsiveness values will determine the most sensitive and responsive measures relative to all study outcomes, versus a significance testing approach in which standardized/conventional threshold values are used to make decisions regarding significance. Sensitivity and responsiveness information will determine which outcomes are most impacted by MBRT for retention in a future full-scale multi-site efficacy trial. Benchmarks for equivalence across sites will be evidenced by: a) qualitative themes that suggest experiential continuity across sites, and b) equivalence in outcome measure response distributions, reliability estimates, and intraclass correlations.

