*Informed Consent.* Study staff will obtain informed consent via REDCap from all participants prior to screening and baseline data collection. The consent form will include information about randomization, release of information (including data from PPB and APD databases), researchers' responsibilities regarding records collected, DHHS certificate of confidentiality, registration with clinicaltrials.gov, and permission to audio and video record sessions.

*Randomization.* Study staff not involved in data collection will randomly assign participants to condition using SPSS and REDCap, stratifying for gender, using a permuted-block randomization procedure frequently used in MT trials to ensure balance within strata and across groups. The study statistician will create an allocation table using SPSS, and upload it to REDCap, which will be used to implement the randomization procedure.

Following completion of the baseline online survey and confirmed completion of the dried blood spot sample, participants will be assigned using a 2:1.5:1 ratio (MBRT = 47; SME = 35; NIC = 22), allowing more robust evaluation of measure sensitivity and responsiveness as well as more accurate parameter estimation for the MBRT group. **Randomization will occur separately at each site to ensure equal ratios at all sites across the three arms.**

Participants will be notified of group assignment via phone call by a study team member. Participants assigned to MBRT and SME conditions will receive emailed information regarding course structure, dates/times, and class format. All participants will be provided information on assessment timeline, reminder calls they will receive, and contact information for the research team. Participants assigned to SME or NIC will be offered an opportunity to attend an MBRT course after the final 12-month follow-up collection of departmental excessive use of force data.

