### **Randomization**

Immediately following completion of the Zoom-facilitated baseline assessment session, and confirmed completion of the dried blood spot sample, study staff not involved in data collection will randomly assign participants to condition using SPSS and REDCap. The study statistician will create an allocation table using SPSS, and upload it to REDCap, which will be used to implement the randomization procedure for all sites. All trial randomization codes will be stored within REDCap, which is a secure (HIPAA-compliant) internet-based survey and data management software system housed on a secure server at Oregon Health and Science University.

Participants will then be notified via phone of group assignment by a study team member. Participants assigned to MBRT and SME conditions will receive emailed information regarding course structure, dates/times, and class format. All participants will be provided information on assessment timeline, reminder calls they will receive, and contact information for the research team. Initiation of study intervention will be between 1 and 21 days. Participants assigned to SME or NIC will be offered an opportunity to participate in an MBRT course after the final 12-month follow-up collection of departmental excessive use of force data. Participants in all conditions will have access to resources provided by PPB, APD or MPD, including counseling services.

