## 9.2 Sample Size and Randomization

Our sample size estimate is derived from a recent conceptual framework and systematic analysis for conducting a feasibility trial in preparation for a future fully-powered efficacy RCT, as well as best practices and suggestions for extending CONSORT guidelines to feasibility trials. Sample sizes of 12-25 participants per arm are recommended to optimize estimation of group means and variability without oversampling in terms of diminishing returns in parameter estimation, and to provide reasonably precise information in terms of confidence intervals around retention rates. This range is consistent with the median treatment arm size of 18 found in a systematic review of feasibility trials, and is sufficient to assess our primary goals of optimizing study procedures and obtaining data for parameter estimation, measure sensitivity, and measure responsiveness. Given the optimization aim of our study, we did not conduct an a priori power analysis based on effect sizes and a variance inflation factor to estimate the needed sample size. Our study will provide estimates of means and variability (including intraclass correlations) that we will use for an a priori power calculation for sample size estimation in a future fully-powered efficacy RCT. Consistent with guidelines on the NIH Research Methods Resources Webpage, the proposal for the future fully-powered efficacy RCT will include a sensitivity analysis that reflects the impact of potential differences between the estimate and realized value of the intraclass correlation, the number of clusters per arm, and size and variability of those clusters, based on the data we obtain in this study.

Measure sensitivity to our study arms will be assessed by examining relative efficiency; more specifically, by dividing the *F*-value for each behavioral, physiological, and self-report outcome by the largest *F*-value among the outcomes. To generate the *F*-values for relative efficiency comparisons, we will conduct a one-way between-subjects Analysis of Variance for each outcome for MBRT vs. SME and MBRT vs. NIC. To adjust for non-ignorable clustering in order

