### **9.3 Definition of Populations**

Our sensitivity and responsiveness analyses will utilize an ITT approach. If attrition occurs, the study statistician will review the reasons for withdrawal to determine if missing data are missing completely at random (MCAR), missing at random (MAR), or missing not at random (MNAR). If data are MCAR, then we will use a complete-case approach to estimate parameters and conduct sensitivity and responsiveness analyses. If missing data are MAR or MNAR, we will employ a multiple imputation approach to impute data before estimating parameters and conducting sensitivity and responsiveness analyses. We will also estimate parameters and conduct sensitivity and responsiveness analyses using a complete-case approach for comparison purposes.

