## **9.6 Data Analyses**

### Quantitative:

Following best practice guidelines including CONSORT feasibility guidelines and past research, we will measure sensitivity (using a relative efficiency approach) and

responsiveness to change (examining within-group change over time). Relative efficiency analyses will be used to establish that our outcome measures are sensitive to differences between our treatment arm of focus (MBRT) and our other two arms - an active control arm (SME) and a no-treatment control arm (NIC). Therefore, sensitivity analyses will focus on assessing the degree to which outcomes are sensitive to study arms and not whether change is significant. Sensitivity to differences for MBRT compared to SME and NIC will be assessed by examining the relative efficiency of each outcome variable for MBRT versus SME and NIC separately. We will calculate the relative efficiency for MBRT versus SME by conducting one-way, between-subjects Analysis of Covariance (ANCOVA) analyses with MBRT versus SME as the independent variable and each outcome variable at post-training as the dependent variable; we will include study site and gender as covariates. We will also conduct ANOVAs using the same independent and dependent variables to ensure that all inferential tests are conducted and identify any potential Type II Errors among the ANCOVAs. We will then divide the *F*-statistic for each behavioral (BlueTeam/departmental use of force; individual indicators of use of force as well as a composite score of use of force using the individual indicators), physiological (C-RP, IL-6, IL-10, TNF- $\alpha$ ), and self-report (aggression, alcohol misuse, depression, suicidal ideation, trauma symptoms, burnout, and psychological resilience) outcome by the largest *F*-statistic among these analyses, such that the larger the number, the more sensitive that outcome is to the impact of MBRT relative to the active control group.

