To calculate the relative efficiency of MBRT versus NIC, we will conduct one-way, between-subject ANCOVAs with MBRT vs. NIC as the independent variable, each outcome variable at post-training as the dependent variable, and gender and study site as covariates. Again, we will also conduct ANOVAs using the same independent and dependent variables to ensure all inferential tests are conducted and identify any potential Type II Errors among the ANCOVAs. We will then divide the *F*-statistic for each behavioral, physiological, and self-report outcome by the largest *F*-statistic among these analyses; again, the larger the number, the more sensitive the outcome is to MBRT relative to the no-treatment control group. These sensitivity analyses will allow assessment of which behavioral, physiological, and self-report outcomes are most sensitive to MBRT.

Responsiveness to change across time will be assessed in the MBRT arm for behavioral, physiological, and self-report outcomes by: 1) calculating and comparing standardized mean responses (SMR) for outcomes by subtracting the baseline mean response for each outcome from the post-intervention mean response for that outcome, and dividing by the standard deviation of change for that outcome; 2) calculating and comparing partial correlation coefficients (adjusting for study site and gender) between a global impression of change measure that captures the subjective experience of changes in stress, job performance, and resilience at post-intervention and residualized change scores (baseline to post-intervention) for each self-report outcome. For both SMR values and correlation coefficients, the higher the absolute value, the more responsive the outcome is to change across time in the MBRT arm. We will conduct additional correlation analyses using the same variables without adjusting for study site and gender to identify any potential Type II Errors among the partial correlations.

In addition, we will examine data for any indications of systematic site differences. Using baseline data (where sample size will be greatest) and pooling arms, since no treatment differences are expected at baseline, distributions of standardized responses on outcome measures will be summarized, graphed, and compared across sites. Key parameters, reliability

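### The between-arm models that rank the outcomes leave out each outcome's own baseline score, which makes the F-values noisier than they need be

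*Combined protocol and SAP*

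**What the plan says.** For MBRT vs SME, section 9.6 specifies an ANCOVA with "each outcome variable at post-training as the dependent variable; we will include study site and gender as covariates". For MBRT vs NIC it specifies "each outcome variable at post-training as the dependent variable, and gender and study site as covariates". Section 9.2 names the same two covariates and says the resulting F-values should reflect group differences as precisely as possible. Each F is divided by the largest F in its comparison. ANOVAs without covariates are added to look for possible Type II errors.

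Section 9.6 lists 12 outcome headings: seven self-report, four blood-spot and use of force. Section 6.2.2 schedules a baseline for the first eleven. Randomization waits for them: "Following completion of the baseline online survey and confirmed completion of the dried blood spot sample" (section 4.3) and "Immediately following completion of the Zoom-facilitated baseline assessment session, and confirmed completion of the dried blood spot sample" (section 6.2.2).

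Baseline scores are used in only two places, both in section 9.6: the responsiveness statistics, within the MBRT arm, and a check for site differences with arms pooled.

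The results matter for the next trial. Section 1.1, Objective 4, says: "Sensitivity and responsiveness information will determine which outcomes are most impacted by MBRT for retention in a future full-scale multi-site efficacy trial". Section 9.2 adds: "Our study will provide estimates of means and variability (including intraclass correlations) that we will use for an a priori power calculation".

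**The concern.** An outcome's own baseline is normally its strongest available predictor. If it is left out, chance differences between arms at baseline carry through to the post-training difference and so to F. The plan makes no significance decision, but the F ratios, together with the responsiveness statistics, decide which outcomes are carried forward. Noise in F therefore becomes noise in outcome selection. The responsiveness statistics do not make up for this, because they use baseline in the MBRT arm only and say nothing about the contrast with SME or NIC.

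Two smaller points go with it:

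- A gap between the ANOVA and ANCOVA results cannot identify a Type II error, because the true difference is unknown. The ANOVAs are a sensitivity analysis.
- Section 9.2 does not list r among the quantities to be estimated for the next power calculation. That calculation will need r if the next trial adjusts for baseline.

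**Working it through.** **Inputs from the documents.** N = 104, allocation 2:1.5:1, arms of 47, 35 and 22 (section 3); 20% attrition (section 9.2). The ratio gives 104 × 2/4.5 = 46.2, 104 × 1.5/4.5 = 34.7 and 104 × 1/4.5 = 23.1, so the stated arm sizes reproduce to within about one participant. After attrition: 47 × 0.8 = 37.6, 35 × 0.8 = 28.0 and 22 × 0.8 = 17.6, taken as 38, 28 and 18.

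**Assumed, because the documents do not give them.** r of .3, .5 and .7, and the effect sizes and correlations in the ranking exercise below.

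**Precision.** Adding the baseline multiplies residual variance by (1 − r²). In SD units:

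half-width = t(.975, df) × √(1/n₁ + 1/n₂) × √(1 − r²)

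The planned model uses five parameters (intercept, arm, two for site, one for gender) and has no r term. The adjusted model uses six. Residual df go from 61 to 60 (38 vs 28) and from 51 to 50 (38 vs 18). √(1/38 + 1/28) = 0.249 and √(1/38 + 1/18) = 0.286.

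| | planned | r = .3 | r = .5 | r = .7 |
|---|---|---|---|---|
| Avoidable variance share, r² | – | 9% | 25% | 49% |
| Half-width, MBRT vs SME | 0.498 | 0.475 | 0.431 | 0.356 |
| Half-width, MBRT vs NIC | 0.574 | 0.548 | 0.498 | 0.410 |

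**F-values.** The non-centrality of F is n₁n₂/(n₁ + n₂) × d², divided by (1 − r²) once baseline is in the model. At an assumed d = 0.5, MBRT vs SME gives 16.12 × 0.25 = 4.03, rising to 4.03/0.75 = 5.37 at r = .5 and 4.03/0.51 = 7.90 at r = .7. For MBRT vs NIC the figures are 3.05, 4.07 and 5.99.

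**Ranking.** Simulated trials had 12 outcomes, one with d = 0.5 and eleven with d = 0.2, and inter-outcome correlation .3. Site (50/25/25%) and gender (20% women) were in every model with no effect of their own. Each scenario had 10,000 trials (Monte Carlo error about 0.5 points). The table shows how often the truly best outcome has the largest F, planned → baseline-adjusted.

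| | MBRT vs SME (38 vs 28) | MBRT vs NIC (38 vs 18) |
|---|---|---|
| all r = .3 | 41 → 43% | 33 → 35% |
| all r = .5 | 40 → 48% | 32 → 39% |
| all r = .7 | 40 → 59% | 33 → 49% |
| best r = .3, others .7 | 40 → 33% | 34 → 28% |

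With best r = .7 and others .3 (38 vs 28) the figure is 41 → 67%.

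**Mixed covariate sets.** If the best outcome is left unadjusted and the others are adjusted, it ranks first in 37% of trials when the others have r = .5 and in about 29 to 32% when they have r = .7 (38 vs 28).

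**Clustering in intervention groups.** With an assumed ICC of .05 in four MBRT and three SME groups (6,000 trials, 38 vs 28), the pattern is the same: 33 → 37% at r = .5, 32 → 43% at r = .7, and 32 → 21% with best r = .3 and others .7. Repeat runs agree within about two points.

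**The case against.** The strongest reply is that nothing in the plan is invalid. Randomization keeps the contrasts unbiased on average, no test result is acted on, and this is a feasibility study without a primary outcome. Section 9.1 also defines sensitivity as the between-group difference at the end of MBRT. A baseline-adjusted F ranks by that difference divided by √(1 − r²), so it rewards stable measures and is partly a different target. With equal d = 0.4, an outcome with r = .8 outranks one with r = .3 in 50% of simulated trials without adjustment and in 74% with it (38 vs 28). The gain can also vanish: with r = .5 for the best outcome and .7 for the others, the figures are 41% and 40%. Finally, r for the MBRT arm can be recovered from the baseline, post and change SDs.

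Most of this stands, and it is why the planned ranking should be kept and not replaced. It does not justify leaving the baseline out altogether. The plan wants F-values as precise as possible, and one degree of freedom is a small price. Where r varied at random between .3 and .7, adjustment still raised the figure from 39% to 49%. A second ranking does leave open which one prevails when they disagree. But the plan already has two comparisons, ANOVA and ANCOVA F-values, standardized mean responses and correlations, with no rule for combining them. Recovering r in one arm is possible, but reporting it directly is simpler and covers all arms.

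**Conclusion.** The concern holds as a matter of precision, not of bias or invalidity. The omission is explicit and consistent across sections 9.2 and 9.6. Its size depends on r: small near .3 (half-width 0.50 to 0.48 SD for MBRT vs SME) and material from about .5 (0.43 SD, or 0.36 at .7). The effect on the ranking also rests on the assumed effects and correlations, and it can go either way when r differs between outcomes. Under most of these assumptions the best outcome ranks first in fewer than six trials in ten, adjusted or not, so neither ranking should be read alone. The change is recommended but not essential to the trial's validity.

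**What to change.** In sections 9.2 and 9.6, state the following:

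- For each comparison, relative efficiency is reported in two sets: (A) ANCOVA with site and gender, for all outcomes; (B) ANCOVA with site, gender and the baseline value of the same outcome.
- Within each set, every F is divided by the largest F in that set. Only outcomes analysed with the same covariates are compared.
- r is reported for each outcome beside both sets, because adjustment raises the F of more stable measures.
- Use of force enters set B only if a pre-baseline count comparable with the follow-up count is defined; otherwise it is ranked in set A only. Section 1.1, Objective 2, allows "1 month to assemble pre-baseline, and 1 month to assemble at 12-month follow-up", and section 6.2.4 fixes collection at day 360, but neither defines a counting window.
- ANOVAs without covariates are a sensitivity analysis. The Type II error wording is removed.

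In section 9.3, add that a missing baseline covariate is imputed whatever the missingness class. The current rule is "If data are MCAR, then we will use a complete-case approach to estimate parameters". In set B that would drop randomized officers who have a post-training score but lack a baseline value. Such gaps can arise from omitted items or failed assays even though randomization waits for baseline completion; section 1.1, Objective 2, expects up to 15% missing data from omitted or refused measures.

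**Cost.** One residual degree of freedom per set B model, a second table of ratios, a column for r, a sentence on missing baselines, and a rule for the use-of-force baseline window. The self-report and blood-spot baselines need no new collection.

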#### **Design and Outcomes**

The study will use a randomized multi-site (Portland, Albuquerque, Madison) clinical trial assessing feasibility and across-site equivalence of all study procedures. Three study arms include MBRT, an attention control (SME), and a no-intervention control (NIC). Outcomes include physiological, behavioral, and psychological indices of officer wellbeing, resilience, and excessive use of force in law enforcement officers.

Participants will complete baseline, post-intervention, and 3- and 6-month follow-up assessments. Assessments include self-report measures, a computerized attention task, and a self-administered dried blood spot test. Participants will be invited to participate in a post-intervention telephone feedback interview. Twelve-month departmental excessive use of force data will be collected from police department databases, and will involve neither direct participant interaction nor compensation.

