12-month Followup (must occur on target date, which is 360 days from the end of the intervention period):

- Excessive Use of Force (Individual-level LEO excessive use of force (i.e., aggressive drawing and discharge of weapons, vehicle rams, illegal takedowns, administrative and citizen complaints)
  - BlueTeam^96 Database and/or other departmental data

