## **9. STATISTICAL CONSIDERATIONS**

### **9.1 General Design Issues**

Our analytic aim is to obtain information to estimate group means, variability, and confidence intervals, identify primary and secondary outcomes, and conduct an a priori power calculation for sample size estimation for a future fully-powered efficacy RCT. Our study aims to optimize measurement by empirically assessing the sensitivity and responsiveness of conceptually well-justified candidate measures for the future trial. Since this is not an efficacy study, no primary or secondary hypotheses have been proposed to test the impact of MBRT on outcomes; however, results from this study will be used to determine primary and secondary outcome categories for the future trial.

All of the self-report measures in this study have been validated and found to be reliable in past research. The physiological measures in this study have been validated and found to be reliable methods of assessing relevant biomarkers in past research. The behavioral measure that will be used in this study is a standardized tracking system that integrates officer, administrator, and citizen data and is considered the current “gold standard” for assessing LEO use of force. An important objective of this study is to demonstrate the potential utility of this behavioral measure as a research outcome. Preliminary review of these data suggest there is sufficient variability in departments at all study sites; however, to our knowledge, the sensitivity to between-group differences and responsiveness to changes during an intervention have not yet been assessed.

Our design is an individually-randomized group treatment trial with three arms (MBRT, SME, and NIC). This design was chosen in order to assess the sensitivity of outcome measures to between-group differences at the end of MBRT and responsiveness to changes in individual LEOs during the course of MBRT. Inclusion of three arms will document the willingness of LEOs to accept randomization to these treatment options, and enable our study staff to assess and optimize the implementation of all study procedures across a no-treatment control group, an active control group, and a treatment group at multiple study sites. This information will allow us to identify primary and secondary outcomes as well as detect and correct any procedural flaws in order to optimize procedures for a future fully-powered, multi-centered efficacy RCT.

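### Use of force is ranked on a post-training value and a baseline-to-post change, but is collected only before baseline and at 360 days, with no counting dates stated

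*Combined protocol and SAP*

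**What the plan says.** Section 9.6 enters use of force in the relative-efficiency analyses as "individual indicators of use of force as well as a composite score of use of force using the individual indicators". Those analyses take "each outcome variable at post-training as the dependent variable; we will include study site and gender as covariates", first for MBRT against SME and then, with the same timing, for MBRT against NIC. Each F is divided by the largest F to rank the outcomes.

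The second ranking has the same scope: "Responsiveness to change across time will be assessed in the MBRT arm for behavioral, physiological, and self-report outcomes". Its SMR is formed by "subtracting the baseline mean response for each outcome from the post-intervention mean response for that outcome", divided by the standard deviation of change, and a larger absolute value counts as more responsive. Section 9.1 describes matching timing for the design as a whole: "sensitivity of outcome measures to between-group differences at the end of MBRT and responsiveness to changes in individual LEOs during the course of MBRT".

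The collection of the measure is described differently:

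- Section 1.1, Objective 2, allows "1 month to assemble pre-baseline, and 1 month to assemble at 12-month follow-up".
- Section 6.2.4 lists use of force only under "12-month Followup (must occur on target date, which is 360 days from the end of the intervention period".
- The Précis says "Twelve-month departmental excessive use of force data will be collected from police department databases".
- Use of force does not appear in the schedule of evaluations (6.1), the baseline list (6.2.2), or the post-course, 3-month and 6-month lists (6.2.4).

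**The concern.** A questionnaire score or a biomarker has a value on the day it is taken. A count of incidents has a value only over a stated interval, and no interval is given before baseline or afterwards. The month allowed in section 1.1 is time to assemble the data, not a period of counting.

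Two readings are open. Sections 9.1 and 9.6 point to a short interval around the end of training. The Précis and section 6.2.4 point to something at, or covering, 12 months. The choice is left to the analyst, possibly after the data have been seen.

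This matters for the study's own aims. Section 9.1 calls it an important objective to show that this measure is usable as a research outcome, and notes that its sensitivity and responsiveness are untested. Sections 3 and 9.6 use the rankings to choose outcomes for the efficacy trial. If the pre and post counts cover different lengths of time, the SMR will show responsiveness where there is none.

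**Working it through.** The plan gives no incident rate, effect size or power figure for use of force, so there is no figure to reproduce. The rates (0.1, 0.3 and 1.0 per officer-year) and the rate ratio (0.7) below are assumptions for illustration.

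**1. Timing, side by side**

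| Item | Where | Time |
|---|---|---|
| Value used for F | 9.6 | post-training |
| Change used for SMR | 9.6 | baseline to post-intervention |
| First collection | 1.1 | before baseline |
| Second collection | 1.1, 6.2.4 | 360 days after the intervention |
| Post-course collection | 6.1, 6.2.4 | none listed |
| Counting dates, pre or post | anywhere | none stated |

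Section 9.6 has no 12-month analysis. It has none at 3 or 6 months for the other outcomes either, but those have a post-course collection that feeds the rankings.

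**2. Calendar (section 3), with month index = 12 × (year − 1) + month**

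- Cohort 1: post-intervention collection in Year 2 Month 8 (20), 12-month pull in Year 3 Month 8 (32). 32 − 20 = 12 months, which agrees with 360 days.
- Cohort 2: post-intervention collection in Year 3 Months 3-4 (27-28), 12-month pull in Year 4 Month 1 (37). 37 − 28 = 9 and 37 − 27 = 10 months, short of 360 days. Training ends in Month 3, so day 360 falls at about index 27 + 12 = 39, two months after the listed pull.

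**3. SMR with no change in rate**

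Let b and p be the expected counts per officer before and after, each equal to rate × days/365. For independent Poisson counts, SMR = (p − b)/√(p + b). With 360 days before and 56 days (8 weeks) after:

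| Rate per year | b | p | SMR |
|---|---|---|---|
| 0.1 | 0.0986 | 0.0153 | −0.25 |
| 0.3 | 0.2959 | 0.0460 | −0.43 |
| 1.0 | 0.9863 | 0.1534 | −0.78 |

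Equal windows give p = b and SMR = 0. Stable differences between officers would widen the denominator and pull these values toward zero without removing them.

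**4. F noncentrality, 360 against 56 days**

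λ = (m1 − m2)²/(v1/n1 + v2/n2), where m2 = rate × days/365, m1 = m2 × rate ratio, and v = m (Poisson) or m + m²/k (overdispersed, k = 1 or 0.5). Arms are 47 MBRT, 35 SME and 22 NIC, taken in full because section 1.1 targets departmental data for every participant.

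Example: MBRT against SME, 0.3 per year, Poisson, 56 days. m2 = 0.0460 and m1 = 0.0322, so λ = 0.0138²/(0.0322/47 + 0.0460/35) = 0.095. At 360 days λ = 0.613, a ratio of 6.4.

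For a fading effect, the 56-day count keeps the full ratio of 0.7. In the 360-day count the 0.7 applies for the first L days and 1.0 afterwards, so the effective ratio is (0.7L + 360 − L)/360. The ranges cover both comparisons, all three rates, Poisson and both values of k.

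| Effect lasts | Effective ratio over 360 days | λ(360)/λ(56) |
|---|---|---|
| all 360 days | 0.70 | 2.9 to 6.4 |
| 180 days | 0.85 | about 0.7 to 1.5 |
| 90 days | 0.925 | about 0.2 to 0.4 |

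**5. Sparsity**

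At 0.3 per year and no effect, expected events in MBRT/SME/NIC (n × 0.3 × days/365) are 2.2/1.6/1.0 in 56 days and 13.9/10.4/6.5 in 360 days.

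**The case against.** The strongest reply is that the source is a departmental database. If its incidents are dated, one extract at day 360 can supply any window, including one that ends with training. That is a fair limit on the point. A reader might infer that the section 9.6 analyses cannot be run, and the documents do not support that. They also do not say that incidents are dated, or which window would be cut.

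The Précis wording could be taken to mean a 12-month count. Such a count would have no stated start or end date and would not be the post-training value that section 9.6 specifies.

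Section 9.1 proposes no hypotheses and the rankings are descriptive, so no error rate is at stake. That stands and limits the severity. Section 9.1 also reports a preliminary review that found sufficient variability, but it does not say over what period.

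Three stronger readings are tempting and should be resisted:

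- That the first cohort's pull comes 15 months after training. This follows only from the training months listed in section 3 (Year 2 Months 4-5), which conflict with the same section's post-intervention month (Year 2 Month 8). Counted from the latter, the gap is 12 months.
- That the open window by itself would reshuffle the outcome ranking. With arms this small, ranks of F move a good deal from sampling alone even under one fixed window, so such movement cannot be put down to the window.
- That 360 days is the right window. It departs from the timing in sections 9.1 and 9.6, and it gives a smaller F if the effect fades early.

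**Conclusion.** The point holds as an undefined measure with conflicting timing, and it should be fixed. The post-training and baseline-to-post values in section 9.6 do not correspond to any stated collection of use of force, and no counting dates exist. The second cohort's listed pull, 9 to 10 months after its post-intervention collection, conflicts with the 360-day rule.

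The firmest consequence is for the SMR. Raw counts over unequal windows would show change where the rate is constant, and the size shown for 360 against 56 days depends on the assumed rates and on Poisson counts. For the F, even the direction of the difference between windows depends on how long an effect lasts, which the documents do not say. All magnitudes are illustrations under assumed rates and a rate ratio of 0.7. The textual finding does not rest on them.

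**What to change.** Before outcome data are seen, add to section 9.6:

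- The start and end dates of the pre-baseline count and of the post count, identical for all arms and both cohorts.
- Equal lengths for the two counts, or both expressed as rates per day at risk. Include a rule for officers whose service is shorter than the look-back, since section 4.1 sets no minimum service.
- Which window feeds the F and the SMR. One option is an end-of-training window cut from dated incidents, which matches sections 9.1 and 9.6. The other is a 360-day window labelled as a 12-month result and shown separately from the post-training ranking.

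Also reconcile the second cohort's 12-month pull in section 3 with the 360-day rule in section 6.2.4.

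The cost is wording and one pull date, with no participant contact. Each department must confirm that incidents are dated and that the look-back can be supplied. A short window will be sparse. A 360-day window answers a longer-term question and dilutes an effect that fades early. The second cohort's pull, and the MBRT offer to SME and NIC officers that follows it (sections 4.3 and 6.2.2), may move about 2 months later.
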